6 OBJECTIVES AND ENDPOINTS

Table 1: Objectives and Endpoints

	Objective	Endpoint	Analysis
Primary	Assess the impact of LCM, LEV or no AED in patients with suspected glioma (WHO Gr I-IV) or brain metastasis on ED visits and readmissions within 30 days of MSR	Percentage of patients with an ED visit or hospital readmission within 30 days of MSR	See Section 13.4
Secondary	Assess the safety and tolerability profile of LCM and LEV	Percentage of patients who experience an adverse event of special interest within the first 30 days after MSR	See Section 13.5
Exploratory	Describe the duration of admission stays among patients treated prophylactically with LCM, LEV, or no AED	Median duration of initial admission stay for MSR	See Section 13.6.1
Exploratory	Describe the number of provider communications (email, telephone, or additional clinical visits) among patients treated prophylactically with LCM, LEV, or no AED	Frequency distribution for the number of provider communications (email, telephone, or additional clinical visits) that occurred within 30 days of MSR.	See Section 13.6.2
Exploratory	Describe the usage of intraoperative AED	Percentage of patients requiring intraoperative AED	See Section 13.6.3
Exploratory	Assess the impact of LCM, LEV, or no AED on post-procedure seizure occurrence	Percentage of patients experiencing post-procedure seizures during the 30-day post-operative phase.	See Section 13.6.4
Exploratory	Describe the frequency of changes in AED dosage, type of AED, addition or discontinuation of AED	The frequency of changes in dosages, type of AED, addition or discontinuation of AED that occur within 30 days of MSR	See Section 13.6.5
Exploratory	Evaluate patient risk factors for post-procedure seizure	Statistically significant association of specific risk factors with rate of post-procedure seizure during the 30-day post-procedure phase	See Section 13.5.6

7 INVESTIGATIONAL PLAN

7.1 Study Design

The protocol will assess the need for AED prophylaxis during the post-procedure period in patients undergoing MSR for a suspected diagnosis of glioma (WHO grade I-IV) or brain metastasis. Patients (n=232) will be consented and randomized at their pre-operative assessment, either at their pre-operative clinic visit or in the ED, if that is the time of their initial presentation prior to surgery. There will be three arms to the study – patients will be randomized to LCM, LEV, or control (no AED). Randomization will be stratified by suspected grade (LGG vs HGG). The AED can be initiated anytime within 48 hours before a MSR incision.

Patients already on AEDs specifically to treat seizures will be excluded. Those patients taking AEDs for any diagnosis other than seizures will be included (e.g. Gabapentin for neuropathic pain, Topiramate for migraine, benzodiazepines as sleeping aid, etc).

Patients taking AEDs for seizure prophylaxis and without clear history of seizures will be included. If already on LEV and randomized to LCM and vice versa, patient will be cross-taper, a week prior to surgery, as follows:

- If on LCM 100mg BID and need to taper to LEV:
 - Start LEV, reduce LCM to 100/50 x 2 days, then 50/50 x 2 days, then 50 daily x 2 days, then off
- If on LCM and need to taper off:
 - Reduce LCM to 100/50 x 3 days, then 50/50 x 3 days, then 50 daily x 3 days, then off

- If on LEV and switch to LCM:
 - Start LCM, reduce LEV to 1000/500mg x 2 days, 500/500mg x 2 days, 500 daily x 2 days, then off
- If on LEV and need to taper off:
 - Reduce LEV to 1000/500 x 3 days, then 500/500 x 3 days, then 500 daily x 2 days, then off

Patients consented less than a week prior to surgery, who were on LCM and get randomized to LEV (or vice versa), will start the new medication, cut their current regimen by half, and stop the day of surgery.

Doses will be either LCM 100mg twice a day (BID) (Arm A), LEV 1000mg BID (Arm B), or no AED (Arm C). If a patient is randomized to Arm C and undergoes tumor mapping, the patient is allowed to receive one dose of AED in the operating room. If a patient is randomized to Arm A or Arm B and takes the morning dose of their AED, they do not need an intra-operative dose of AED. If a patient has a seizure during the post-procedure period, AEDs will be adjusted at the discretion of the treating physician. However, if a patient has intolerable side effects, patients will be changed to a different dose of the same medicine before consideration of another AED [i.e., BID to four times a day (QID) dosing if patient experiences diplopia on LCM].

Patients with high-grade tumors (newly-diagnosed or transformed) will be treated with standard radiation and temozolomide therapy per the Stupp protocol^{25,70}. For these patients, an AED taper will be initiated at the first clinic visit after completion of radiation. For patients with a low-grade tumor or recurrent disease of any grade, an AED taper will be initiated at the first scheduled post-procedure visit, approximately 6-10 weeks after the operation. LCM will be tapered by 100mg a week one week at a time. LEV will be tapered 500-1000mg one week at a time.

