10.2 Study Period

Day 0 and prior (diagnosis): occurring at least within 48 hours prior to MSR

- Randomization
- Initiate AED, per Section [7.1.1](#) (LCM 100mg BID or LEV 1000mg BID)
- Characterize seizure type, if applicable, (i.e., simple partial, complex partial, or generalized)

Week 0-6

- Management of AEDs for any seizure events or adverse events will be left at the discretion of the treating physician. If side effects occur, adjusting dosing of current AED before changing AEDs is recommended.

Week 6-10: at the first planned post-procedure visit (LGG or brain metastasis) or first visit after radiation (HGG), the following study endpoint data will be collected only for the 30-day post-procedure time period

- Collection of calendar, if not already obtained from the REDcap database
- CMP and CBC with differential to assess resolution of toxicity
- AESI (please see Section [7.1.4](#))
- Number of readmissions, ED visits, provider communications during the 30-day post-procedure phase
- Number of dose adjustments, additions or discontinuations of AED(s) during the 30-day post-procedure phase
- Initiate weaning of the AED per discretion of the treating physician, for example:
 - LCM 100/50mg x1 week, 50/50mg x 1 week, 50mg daily x 1 week, then off
 - LEV 1000/500mg x1 week, 500/500mg x 1 week, 500mg daily x 1 week, then off

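### Protocol 7.1 does not fit the taper to no AED into the week before surgery and gives no short-notice rule for Arm C, so some controls may still be on AED at incision

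*Protocol*

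**What the plan says.** All of the following is in Protocol 7.1 (Study Design) unless stated otherwise.

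- **Eligibility.** "Patients taking AEDs for seizure prophylaxis and without clear history of seizures will be included". Exclusion criterion 2 in 9.1.2 and the SAP's exclusion criteria say the same. Such patients can be randomized to any arm.
- **Lead-in.** For a patient on one study drug and randomized to the other, the "patient will be cross-taper, a week prior to surgery, as follows". Four schedules follow in one list.
- **Switches.** From LCM: "Start LEV, reduce LCM to 100/50 x 2 days, then 50/50 x 2 days, then 50 daily x 2 days, then off". From LEV: "Start LCM, reduce LEV to 1000/500mg x 2 days, 500/500mg x 2 days, 500 daily x 2 days, then off".
- **Taper to no drug.** From LCM: "Reduce LCM to 100/50 x 3 days, then 50/50 x 3 days, then 50 daily x 3 days, then off". From LEV: "Reduce LEV to 1000/500 x 3 days, then 500/500 x 3 days, then 500 daily x 2 days, then off".
- **Short notice.** A separate rule applies to "Patients consented less than a week prior to surgery, who were on LCM and get randomized to LEV (or vice versa"). It does not mention patients randomized to no AED.
- **Enrolment timing.** Sections 7.1 and 7.1.1 allow enrolment at the pre-operative visit or in the emergency department at first presentation. Table 2 places screening up to 48 hours before resection. Section 10.2 lists randomization under Day 0 and prior, "occurring at least within 48 hours prior to MSR".
- **AED allowed in Arm C around surgery.** The only stated allowance is one operating-room dose when tumor mapping is done.

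**The concern.** Arm C is the only control group and, under 1:1:2 allocation, half the trial. A patient who arrives on prophylactic LCM or LEV and is randomized to Arm C has to stop the drug, and the instructions for doing so either conflict or are missing. If the one-week timing governs the whole list, the two taper-off schedules overrun it. If it governs only the switches, the taper-off schedules have no start time. Under either reading, a control consented less than a week before surgery has no instruction.

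Two things are at stake. Staff would have to improvise a drug withdrawal just before brain surgery, possibly differently for each patient. And controls still taking AED at surgery would pull the Arm C event rate toward the AED rate under an intent-to-treat analysis. That lowers power and makes the interim rule for accepting the null (Z at or below 0.48887, Protocol 13.7) somewhat easier to meet.

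**Working it through.** **Step 1. Length of each schedule (Protocol 7.1) against 7 days**

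| Schedule | Sum of steps | Against 7 days |
|---|---|---|
| LCM to LEV | 2+2+2 = 6 | fits |
| LEV to LCM | 2+2+2 = 6 | fits |
| LCM to none | 3+3+3 = 9 | 2 days over |
| LEV to none | 3+3+2 = 8 | 1 day over |

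If the taper starts 7 days before surgery, surgery falls on taper day 8. LEV is then still taken on surgery day (day 8 of 8), and LCM on surgery day and the next day (days 8 and 9 of 9). With k days' notice, and the listed schedule followed, the overlap counted from surgery day is 9 − k days for LCM and 8 − k days for LEV. It therefore lengthens as notice shortens, up to 9 days if an LCM taper began on surgery day.

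**Step 2. Reproduce the plan's sample size**

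Inputs from Protocol 13.7 and 13.8: P1 = 0.12, P2 = 0.25, 116 per group, interim at 58 per group. At the interim, reject above 2.31015 and accept at or below 0.48887. At the final analysis, reject above 1.63351.

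With unpooled variance, v = 0.12×0.88 + 0.25×0.75 = 0.2931.
- Interim drift: 0.13/√(0.2931/58) = 1.829
- Final drift: 0.13/√(0.2931/116) = 2.586

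Power = P(Z₁ > 2.31015) + P(0.48887 < Z₁ ≤ 2.31015 and Z₂ > 1.63351), with (Z₁, Z₂) bivariate normal and correlation √0.5. This gives one-sided type I error 0.0500 and power 80.3%. The smallest total that reaches 80% is 232, which is the plan's figure. Pooled variance gives 238.

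**Step 3. Dilution**

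Let f be the share of Arm C still on AED at surgery, and g the fraction of the full AED effect those patients gain. Then P2 = 0.25 − f×g×0.13, with P1 = 0.12 and the design otherwise unchanged. For example, f = 30% and g = 9/30 give P2 = 0.25 − 0.30×0.30×0.13 = 0.2383.

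The documents give neither f nor g, so both are assumptions:
- g = 2/30: surgery day plus one of the 30 follow-up days, the LCM case with a full week's notice.
- g = 9/30: a whole LCM taper falling after surgery begins.
- g = 1: controls behave as if fully treated for 30 days.

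| f | g = 2/30 | g = 9/30 | g = 1 |
|---|---|---|---|
| 5% | 80.1% | 79.4% | 77.1% |
| 10% | 79.9% | 78.4% | 73.6% |
| 20% | 79.5% | 76.4% | 65.8% |
| 30% | 79.0% | 74.3% | 57.0% |

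**Step 4. Interim acceptance of the null**

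The probability is Φ(0.48887 − interim drift).
- No dilution: Φ(0.489 − 1.829) = 9.0%
- f = 30%, g = 9/30: drift 1.681, giving 11.7%
- f = 30%, g = 1: drift 1.329, giving 20.0%

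**The case against.** **The one-week sentence names only switches.** This is true as worded. The taper-off schedules fall under it by their place in the list. On the narrower reading there is no conflict of 9 or 8 days against 7, but the taper to no drug then has no start time. The gap changes form and does not close.

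**A patient consented early enough can finish.** This stands. Section 7.1 sets no maximum lead time, so a patient consented nine or more days ahead could be off drug by surgery. A reader might infer that controls will necessarily be on AED at surgery. The documents do not support that. They show only that it may happen, and they do not say how many patients enter on prophylaxis. Section 5.2.9 describes peri-operative and prolonged post-operative prescribing at the center, which is not the same as arriving at enrolment already on AED.

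**There is no firm 48-hour randomization window.** This stands too. A reader might take Section 10.2 and Table 2 to mean that randomization happens only in the last 48 hours, when no taper could fit. Both can be read as a latest time, and the 48 hours in 7.1 and 7.1.1 limits when AED is started. The separate rule for consent under a week before surgery implies that longer lead times are expected. Late and emergency-department enrolment are nonetheless allowed, so short notice is a foreseeable case.

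**Brief residual exposure is not full treatment.** This also stands. The last taper step, 50 mg LCM or 500 mg LEV daily, is a quarter of the arm's daily dose (50/200 and 500/2000), and the design already tolerates one operating-room dose in Arm C for mapping. The last column of the power table is therefore an extreme, not an expectation.

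**Some of the data are already collected.** Section 7.1.7 records concomitant medication from enrolment through the 30-day follow-up. Protocol 13.6.3 and the SAP's intra-operative AED variable capture use in the operating room. Neither separates a residual taper from an intra-operative dose. The SAP text available for this review ends at a medical-history heading, so it cannot be said that the SAP ignores AED use at baseline.

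**Conclusion.** The point holds as a conflict or gap between stated rules for a foreseeable group: Arm C patients who enter on prophylactic LCM or LEV. The day counts and the absence of an Arm C short-notice rule are certain from the text. That such patients may still be on AED at incision follows if they start the listed taper a week or less before surgery. With a full week the overlap is surgery day for LEV, and surgery day plus the next for LCM. It is longer with less notice.

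The effect on the trial depends on two unknowns, the share affected and how much of the AED effect they gain. For assumed shares of 5% to 30%, the power loss is about a point or less at 2/30 of the effect and up to about six points at 9/30. A reader might infer from the extreme column that the trial stands to fall to 57% power. That needs 30% of controls to behave as fully treated for 30 days, and nothing in the documents supports it. The case for action rests on the unclear instruction to patients and on the low cost of the remedy more than on the power figures.

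**What to change.** 1. Reconcile four items in Protocol 7.1, Table 2 and 10.2: the taper-off lengths, the one-week timing, the short-notice rule and the enrolment timing. One instruction should apply to Arm C patients already on AED, including those consented less than a week before surgery. The clinical team must choose the schedule; none is proposed here.
2. Using the concomitant-medication record (7.1.7), flag for every patient whether a prophylactic AED was in use at entry and whether it was still being taken at incision. Keep the second item distinct from an intra-operative dose.
3. Report the primary result with and without patients who entered on prophylactic AED, as a supportive analysis. Entry status is fixed before randomization, so this split keeps the randomized comparison. AED status at incision arises after randomization and should be described, not used to exclude patients.

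The cost is amendment wording, one flag drawn from data already collected, and one table.

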7.1.1 AED initiation

At study enrollment, patients will be randomized to either LCM, LEV or no AED. Enrollment can occur at the pre-operative visit before MSR or in the emergency room at the time of patient's first presentation. AED can be initiated anytime within 48 hours of the first MSR incision.

7.1.2 AED titration

If a patient experiences seizure during the follow up period, AED doses will be modified per treating physician preferences.

7.1.3 Post-procedure data collection

Approximately 6-10 weeks after the procedure (for LGG or recurrent high grade glioma or brain metastasis) or first visit after radiation [for newly-diagnosed or transformed high grade glioma (HGG)], the following data will be obtained: admission duration for the MSR, any seizure activity, any readmissions, ED visits, and provider communications (telephone, email, and additional clinic encounters, etc.), as well as for tolerance of the AED by clinical history and neurological examination. Reasons for readmission and ED visits will also be noted. All of these data are only obtained if relevant during the 30-day post-procedure time. Patients will be provided a physical calendar to document any of the above, or provided access to the Research Electronic Data Capture™ (REDCap™) calendar, based on the patient's preference.

7.1.4 Adverse Events of Special Interest (AESI)

The occurrence of adverse events of special interest (AESIs) will be recorded only for the 30-day post-procedure phase.

AESIs for this study will be graded using the National Cancer Institute's (NIH) Common Terminology Criteria for Adverse Events (CTCAE) v4 and are the following: any grade of seizure, dizziness, somnolence, cognitive

disturbance, nausea, vomiting, ataxia, nystagmus, suicidal ideation, suicide attempt, anxiety, irritability, depression, psychosis and personality change (e.g. aggression).

7.1.5 Safety Considerations

LEV has even been associated with a greater suicide risk in those with a psychiatric history. The latter risk depends primarily on the psychiatry comorbidities of the patient. The potential risk for the patient will be discussed in detail with the patient and family. See Section [5.2.5](#) for additional AED side effects.

7.1.6 Missed Doses

Missed doses will be taken as soon as remembered. Patients will be provided a calendar to track doses taken in order to determine compliance.

7.1.7 Concomitant Medications

Given the lack of significant drug-drug interactions with new generation AEDs, concomitant medications will not be limited. If needed, patients will be initiated on chemotherapy, radiation therapy and corticosteroids, per standard of care. Concomitant medications will be recorded by the study team from time of enrollment and during the 30-day follow up.

7.1.8 Randomization

Upon consent, patients will be randomized in REDCap™ to receive either LCM, LEV, or no AED. Randomization will be stratified by suspected histologic grade (LGG vs HGG) based on MRI review by the treating neurosurgeon and/or neuro-oncologist. A stratified permuted block randomization algorithm will be used assign patients to treatment arms.

7.2 Rationale for Selection of Dose and Treatment Duration

Dosing was based on standard dosing approved by FDA for each AED. Treatment duration of approximately 6 to 10 weeks correlates with when the patients will most likely be guaranteed follow up after surgery, an optimal time to evaluate whether an AED should be continued or not.

7.3 Definition of Evaluable Subjects, On Study, and End of Study

Any patient that has been consented and randomized to the trial will be included in all analyses with the exception of those deemed non-evaluable as described in Section [10.5.2](#).

Subjects will be considered on study once they have signed the informed consent form.. Subjects will be considered off study when they have been evaluated approximately 6 to 10 weeks post MSR and once their calendar has been submitted.

7.4 Early Study Termination

This study can be terminated at any time for any reason by the PI-sponsor. If this occurs, all subjects on study should be notified as soon as possible. Additional procedures and/or follow up should occur in accordance with Section [10.3](#).

8 STUDY DRUGS

8.1 Names, Classification, and Mechanism of Action

See Section [5.2](#)

8.2 Packaging and Labeling

Package Inserts are uploaded in eIRB Section 8.

8.3 Supply, Receipt, and Storage

Local Pharmacy and/or Duke Hospital Pharmacy.

8.4 Dispensing and Preparation

Medications will be prescribed for subjects and obtained from the subject's local pharmacy or mail-order pharmacy as per the subject's health insurance plan. Subjects receiving medication after hospital admission will have medication dispensed from Duke Hospital Pharmacy.

9 SUBJECT ELIGIBILITY

9.1.1 Inclusion Criteria

1. Patients with a suspected diagnosis of new, recurrent, or transformed glioma (WHO grade I-IV) or brain metastasis scheduled for MSR at DUMC;
2. Safe for surgery per treating neurosurgeon;
3. Due to the potential implications of the treatment on the developing CNS, all patients must be ≥ 18 years of age at the time of entry into the study;
4. Laboratory Studies:
 - a. Total bilirubin, Serum Glutamic Oxaloacetic Transaminase (SGOT), Serum Glutamic Pyruvic Transaminase (SGPT), Alkaline Phosphatase (ALK) ≤ 1.5 x upper limit of normal (ULN)
 - b. Creatinine ≤ 1.5
5. A signed informed consent form approved by the Duke University Institutional Review Board (IRB) will be required for patient enrollment into the study. Patients or their Legally Authorized Representative (LAR) must be able to read and understand the informed consent document and must sign the informed consent indicating that they are aware of the investigational nature of this study. Treating physicians at the time the protocol is presented are able to determine based on their clinical judgment whether patients lack the capacity and require a LAR to sign the consent form.
6. Patients of child bearing potential or with partners of child-bearing potential must agree to practice recommended contraceptive methods to prevent pregnancy during treatment and for 1 month after the last dose of AED for women and men.

9.1.2 Exclusion Criteria

1. Pregnant or need to breast feed during the study period (Negative urine β -HCG test required), or unable to maintain use of contraception while on study and for 1 month after the last dose of AED;
2. Patients already on AED(s) specifically to treat seizures will be excluded. Those patients taking AEDs for any diagnosis other than seizures will be included (e.g. Gabapentin for neuropathic pain, Topiramate for migraine, benzodiazepines as sleeping aid, etc). Patients taking AEDs for seizure prophylaxis and without clear history of seizures will be included;
3. Known history of epilepsy/seizure disorder;
4. Known history of dependency/abuse of psychopharmaceuticals, alcohol, illicit drugs or narcotics;
5. Any significant medical or psychiatric illness that cannot be adequately controlled with appropriate therapy or would compromise the patient's ability to tolerate therapy, per the discretion of the treating investigator;
6. Known allergy to LCM or LEV.

10 SCREENING AND ON-STUDY TESTS AND PROCEDURES

Table 2: Schedule of Events

Description	Screening at pre-operative visit up to 48 hours prior to MSR	First post-procedure visit (LGG) or first visit after radiation (HGG)
Week		6-10*
Day	0	
General Evaluations		
Physical Exam	X	X
Neurologic Exam	X	X
Evaluation as candidate for MSR	X	
Adverse Events		X
Laboratory Evaluations		
CBC with differential	X	X
CMP	X	X
Urine Pregnancy Test	X	
Disease Evaluations		
Seizure-related readmissions, ED visits, provider communications, duration of admission for MSR		X

*While patients will be assessed between 6-10 weeks post-procedure, only endpoint data pertaining to the first 30 days post-procedure will be recorded in the source documentation and in the database.

10.1 Screening Evaluations

The baseline physical and neurologic examination along with standard of care blood work will be performed and documented by the clinical team and verified by the study team during the pre-operative clinic (or ED) visit. All subject screening data is standard of care evaluations that occur for all patients being seen for possible MSR of suspected LGG or HGG (newly-diagnosed, recurrent, or transformed.) An informed consent must be signed by the patient before any research-related procedure takes place.

Pre-treatment evaluations will include the following:

- History and physical exam, as part of pre-operative evaluation
- Laboratory Evaluations:
 - CBC with differential
 - CMP
 - Urine pregnancy test, if appropriate (serum pregnancy if unable to obtain urine)

If a subject is found to be ineligible to participate in the study, minimal records regarding the subject and the reason for screen failure will be retained in the study database.

The only data collected pertains to the 30-day post-procedure period, however, data may be delayed in collecting due to the standard of care clinic visit schedule.

